4.3 JUSTIFICATION FOR DOSE

The nasal cavity is innervated by sensory nerves via the trigeminal nerve. We believe using a standardized dose of bupivacaine 1.3% combined with 2mg preservative-free dexamethasone to areas on or around the nasal cavity that are innervated with sensory nerves will improve post-operative pain control results. A max amount of 20 mL will be injected into each study participant. The control group will receive no injection.

4.4 END OF STUDY DEFINITION

A participant is considered to have completed the study if he or she has completed all phases of the study including the last visit or the last scheduled procedure shown in the Schedule of Activities (SoA), Section 1.2.

The end of the study is defined as completion of the last visit or procedure shown in the SoA in the trial.

5 STUDY POPULATION

5.1 INCLUSION CRITERIA

In order to be eligible to participate in this study, an individual must meet all of the following criteria:

1. Age 18 years or older
2. Ability to speak English
3. Ability to sign informed consent form
4. Ability to comply with all study procedures
5. Diagnosis of chronic rhinosinusitis
6. Scheduled to receive functional endoscopic sinus surgery (FESS) at UAB

5.2 EXCLUSION CRITERIA

An individual who meets any of the following criteria will be excluded from participation in this study:

1. Current use of opioid medication
2. Known allergic reactions to components of the study intervention
3. History of IV drug use or abuse
4. History of opioid abuse
5. History of chronic pain disorder
6. Treatment with another investigational drug or other intervention within 30 days

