2.3 RISK/BENEFIT ASSESSMENT

2.3.1 KNOWN POTENTIAL RISKS

All of the drugs to be used in this study are FDA-approved, commonly-used, widely available, generic medications. These drugs will be prescribed at their standard dosing for their approved indications.

As outlined in the package inserts for the medications under study in this protocol, the following adverse reactions have been identified during post approval use. Because these reactions are reported voluntarily from a population of uncertain size, it is not always possible to reliably estimate their frequency or establish a causal relationship to drug exposure.

- *Risks associated with bupivacaine hydrochloride (MarcaineTM):* The most frequently reported adverse reactions are restlessness, anxiety, dizziness, tinnitus, blurred vision, tremors, nausea, vomiting, chills, and constriction of pupils (central nervous system reactions) and depression of the myocardium, decreased cardiac output, heartblock, hypotension, bradycardia, ventricular arrhythmias, including ventricular tachycardia and ventricular fibrillation, and cardiac arrest (cardiovascular system reactions). Other reported reactions include persistent anesthesia, paresthesia, weakness, or paralysis. Allergic reactions are characterized by signs such as urticaria, pruritus, erythema, angioneurotic edema (including laryngeal edema), tachycardia, sneezing, nausea, vomiting, dizziness, syncope, excessive sweating, elevated temperature, and possibly, anaphylactoid-like symptomatology (including severe hypotension). Reactions to MARCAINE are characteristic of those associated with other amide-type local anesthetics. A major cause of adverse reactions to this group of drugs is excessive plasma levels, which may be due to overdosage, unintentional intravascular injection, or slow metabolic degradation. In

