addition to systemic dose-related toxicity, unintentional subarachnoid injection of drug during the intended performance of caudal or lumbar epidural block or nerve blocks near the vertebral column (especially in the head and neck region) may result in underventilation or apnea ("Total or High Spinal"). Also, hypotension due to loss of sympathetic tone and respiratory paralysis or underventilation due to cephalad extension of the motor level of anesthesia may occur. This may lead to secondary cardiac arrest if untreated. Patients over 65 years, particularly those with hypertension, may be at increased risk for experiencing the hypotensive effects of bupivacaine hydrochloride. Factors influencing plasma protein binding, such as acidosis, systemic diseases which alter protein production, or competition of other drugs for protein binding sites, may diminish individual tolerance. Bupivacaine hydrochloride carries a black box warning for cardiac arrest with difficult resuscitation or death during use for epidural anesthesia in obstetrical patients.

- *Risks associated with dexamethasone sodium phosphate injection:* The most frequently reported adverse reactions are anaphylaxis, infection, seizures, hypertension, erythema, rash, urticarial, nausea, vomiting, edema, petechial, ecchymosis, skin pigmentation abnormality, acne, headache, dizziness, vertigo, insomnia, anxiety, and depression.
- *Risks associated with protocol-mandated procedures:*
 - *Surgical procedures:* All surgical procedures will be performed in the routine manner. There will be no additional clinical or surgical risks, other than the normal risks for patients undergoing this type of treatment.
 - *Questionnaires:* Completion of a questionnaire and the questions might make the subject feel uncomfortable or upset. Subjects will have the choice to not answer any such questions.

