2.3.3 ASSESSMENT OF POTENTIAL RISKS AND BENEFITS

Routinely dexamethasone is used for general anesthesia to help decrease inflammation and post-operative swelling. All patients will be screened for any previous reactions to the medications being used in our study. Patient medical records will also be reviewed for past drug allergies. As our study plans to evaluate the local effects of bupivacaine with dexamethasone, we anticipate only mild local reactions, as we will not systemically inject the drugs being used. The risks to participants will likely encounter only local skin reactions to the medications. The information gained will help to possibly standardize how we treat post-operative pain after sinus surgery.

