7.2 PARTICIPANT DISCONTINUATION/WITHDRAWAL FROM THE STUDY

Participants are free to withdraw from participation in the study at any time upon request.

An investigator may discontinue or withdraw a participant from the study for the following reasons:

- If any clinical adverse event (AE), laboratory abnormality, or other medical condition or situation occurs such that continued participation in the study would not be in the best interest of the participant
- Disease progression which requires discontinuation of the study intervention
- If the participant meets an exclusion criterion (either newly developed or not previously recognized) that precludes further study participation
- Non-compliance with follow-up activities

Subjects who sign the informed consent form and are randomized but do not receive the study intervention may be replaced. Subjects who sign the informed consent form, and are randomized and receive the study intervention, and subsequently withdraw, or are withdrawn or discontinued from the study, will be replaced.

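### No documented check before randomization that a participant could receive the injection: allergy is the only drug-safety exclusion, and a later decision to withhold could arise only in the treatment arm

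*Protocol*

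**What the plan says.** **Eligibility.** The only exclusion in 5.2 that concerns the safety of the injected drugs is "Known allergic reactions to components of the study intervention". The other five cover current opioid use, intravenous drug use, opioid abuse, chronic pain and other investigational treatment. Section 2.3.3 matches this: "All patients will be screened for any previous reactions to the medications being used in our study", with a review of records for drug allergies. Section 5.1 sets age as "Age 18 years or older", with no upper limit.

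**Risk.** Section 2.3.1 goes further than allergy. It says "Patients over 65 years, particularly those with hypertension, may be at increased risk for experiencing the hypotensive effects of bupivacaine hydrochloride". Among the causes of excessive plasma levels it lists "unintentional intravascular injection, or slow metabolic degradation"; the second of these is a patient characteristic. It adds that individual tolerance may be reduced by "Factors influencing plasma protein binding, such as acidosis, systemic diseases which alter protein production, or competition of other drugs".

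**Data before allocation.** Section 1.2 places medical history, physical examination, vital signs, height and weight, and a medication review at screening, and randomization on the day of surgery. Section 6.2 allocates a number only once the participant's entry has been confirmed.

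**After allocation.** Section 4.3 states: "The control group will receive no injection". Section 7.2 states: "Subjects who sign the informed consent form and are randomized but do not receive the study intervention may be replaced". Section 7.1 treats anyone discontinued from the intervention as a screen failure, removes that person from the dataset and stops data collection. Section 5.3 defines a screen failure as someone who consented but was not then randomized or entered.

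**The concern.** The protocol names groups at raised risk from the study drug, yet does not say whether they are eligible or when anyone decides that a given participant can be injected. Two things are at stake.

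The first is safety: a participant with a factor named in 2.3.1 can meet 5.1 and 5.2, be randomized and reach the injection without any recorded judgement on that factor.

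The second is bias: if the judgement is made only when the injection is due, it is made with the allocation known and only for people allocated to be injected. A control with the same factor has nothing to withhold and stays in. Removal and replacement under 7.1 and 7.2 would then leave the treatment arm selected on fitness and the control arm not, so randomization would no longer protect the comparison.

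**Working it through.** **Step 1: factors in 2.3.1 set against eligibility**

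| Factor in 2.3.1 | Criterion in 5.1 or 5.2 | Baseline item that could show it |
|---|---|---|
| Allergic reaction | 5.2, criterion 2 | History, record review |
| Age over 65, particularly with hypertension | None; no upper age limit | Demographics, vital signs, history |
| Slow metabolic degradation | None | History |
| Acidosis, or systemic disease altering protein production | None | History |
| Drugs competing for protein binding | None | Medication review |

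Relevant data are collected, but no rule links them to eligibility. Section 6.2 requires entry to be confirmed and does not say what is confirmed.

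**Step 2: can the withdrawal rules act equally in both arms?** The investigator's reasons in 7.2 are not limited by arm. The newly recognized exclusion criterion does not reach these factors, because none of them is an exclusion criterion. The medical-condition reason covers both arms in form, but a bupivacaine risk factor gives little cause to withdraw a control who will not be injected. Withholding or stopping the injection is possible only where one is due.

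**Step 3: what happens next.** A participant never injected falls under the replacement sentence in 7.2, which permits replacement and does not mention deleting data. A participant whose injection is stopped falls under 7.1, which does delete. Either way the arm analysed may differ from the arm randomized. Section 7.1 also applies the term screen failure to a randomized person, which 5.3 does not allow.

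**Step 4: illustrative size.** From 4.1, n = 15 per arm (15 + 15 = 30, which agrees with the stated enrolment). Assumptions not in the protocol: a share u of eligible participants for whom the injection would be withheld or stopped, and a difference of d SD in outcome between them and the rest.

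- Expected number affected in the treatment arm = 15u.
- P(at least one) = 1 − (1 − u)^15.
- Shift in the arm difference if all are replaced by unaffected participants and no control is = u × d.

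| u | Expected | P(at least one) | Shift, d = 0.5 | Shift, d = 1 |
|---|---|---|---|---|
| 5% | 0.75 | 0.537 (54%) | 0.025 SD | 0.05 SD |
| 10% | 1.5 | 0.794 (79%) | 0.05 SD | 0.10 SD |
| 20% | 3.0 | 0.965 (0.9648, so 96%) | 0.10 SD | 0.20 SD |

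**Step 5: scale.** The protocol gives no alpha or power. Assuming two-sided 5% and 80% power, and using the normal approximation, the detectable difference is (1.960 + 0.842) × √(2/15) = 1.02 SD. If three treated participants were lost without replacement it would be (1.960 + 0.842) × √(1/15 + 1/12) = 1.085 SD. Even the largest shift in the table is therefore small beside what 15 per arm can detect. It is systematic, however, and its direction depends on how the affected participants differ from the rest.

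**The case against.** The strongest reply is that 2.3.1 and 5.2 do not conflict. Section 2.3.1 summarises package-insert risks in cautious terms, and describing a risk without excluding everyone who carries it is a legitimate clinical choice. That stands. A reader might infer that the named groups are unfit for the block; the text speaks of raised risk or reduced tolerance and does not call them unsuitable.

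A reader might also infer that the protocol acts on unfitness only in the treatment arm. It says no such thing, and the withdrawal reasons in 7.2 cover any participant. The asymmetry is an inference from the design: only one arm has an injection to withhold.

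The protocol also does more before allocation than a quick reading suggests. History, vital signs and a medication review come at baseline, and 6.2 requires confirmed entry. This weakens the concern, but none of these steps requires a recorded judgement about the injection. The order of the day-of-surgery bullets in 8.1, where medication review comes last, might be read as placing it after the injection. The list is unnumbered and gives no sequence, so it proves little.

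The two harms are also alternatives for any one participant: either the injection is given without a recorded judgement, or it is withheld and the participant may be lost. They cannot be added together, and the figures above describe only the second.

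Finally, removal and replacement under 7.1 and 7.2 would be a weakness whatever the eligibility criteria were. That is true. The missing check is one route by which those rules could act in one arm only.

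**Conclusion.** The point holds in this form: allergy is the only drug-safety exclusion, other risk factors named in 2.3.1 are left unresolved, and no suitability judgement has to be documented before allocation. A decision to withhold or stop the injection made after allocation can fall only on the treatment arm, and 7.1 and 7.2 then let it change who is compared.

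The size is not known. Over assumed shares of 5% to 20% and assumed differences of 0.5 to 1 SD, the shift runs from 0.025 to 0.20 SD, with a 54% to 96% chance that at least one treated participant is affected. These figures rest on assumptions, on every such participant being replaced, and on no control being removed for the same reason. The protocol supports none of these as a forecast. The bias is modest, but it can be avoided at little cost. The safety gap and the conflict between 5.3 and 7.1 do not depend on the assumptions.

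**What to change.** - In 1.2, 6.2 and 8.1, require that before the randomization number is drawn the investigator records, for every participant, that 5.1 and 5.2 are still met and that the participant could receive the study injection if allocated to it. The history, vital signs and medication review already collected can serve as the basis.
- Reconcile 2.3.1 with 5.2: for each factor named, the sponsor states whether it excludes a participant. Which factors should exclude is a clinical decision, and none is proposed here.
- Reconcile 5.3 with 7.1 and 7.2, so that a randomized participant is not reclassified as a screen failure and stays in the dataset in the arm allocated, with any replacement recorded as an addition.
- Reconcile 4.3, which describes 20 mL as a maximum, with 6.1.2, which gives it as the volume. The two must agree; which is right is for the sponsor.

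The cost is an amendment and one checklist item on the day of surgery. The downside is a few more screen failures before randomization and a slightly narrower population.

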5.3 SCREEN FAILURES

Screen failures are defined as participants who consent to participate in the clinical trial but are not subsequently randomly assigned to the study intervention or entered in the study. A minimal set of screen failure information is required to ensure transparent reporting of screen failure participants, to meet the Consolidated Standards of Reporting Trials (CONSORT) publishing requirements and to respond to queries from regulatory authorities. Minimal information includes demography, screen failure details, eligibility criteria, and any serious adverse event (SAE).

5.4 STRATEGIES FOR RECRUITMENT AND RETENTION

Patients who have presented to the UAB Department of Otolaryngology for evaluation and treatment of chronic sinusitis requiring surgery. The Principal Investigator has a practices specifically designated for treating rhinologic disorders, with potential for enrollment. Subjects will be identified from individuals treatment by the investigators in their clinics. Potential subjects will be approached by the Principal Investigator or qualified research staff authorized to conduct the informed consent discussion during their regularly-scheduled clinic visit about participation in the study.

6 STUDY INTERVENTION

6.1 STUDY INTERVENTION(S) ADMINISTRATION

6.1.1 STUDY INTERVENTION DESCRIPTION

Bupivacaine hydrochloride (MarcaineTM) is 2-Piperidinocarboxamide, 1-butyl-N-(2,6-dimethylphenyl)-monohydrochloride monohydrate. The molecular formula is C₁₈H₂₈N₂O with a molecular weight of 288.43.

Dexamethasone sodium phosphate is 9-Fluoro-11 β ,17,21-trihydroxy-16 α -methylpregna-1,4-diene-3,20-dione 21-(dihydrogen phosphate) disodium salt. The molecular formula is C₂₂H₂₈FN₂O₈P with a molecular weight of 516.41.

6.1.2 DOSING AND ADMINISTRATION

Treatment Group: 20 mL of 1.3% bupivacaine with 2 mg dexamethasone injected locally in the location for sensory nerves of the sinus cavities and face during the FESS.

Control Group: No local regional anesthetic will be used during the FESS..

6.2 MEASURES TO MINIMIZE BIAS: RANDOMIZATION

Subjects will be randomized 1:1 (parallel assignment) into the two treatment groups. The next subject to be randomized into a trial will receive the treatment corresponding to the next free number in the randomization schedule. The appropriate number and associated treatment for the next subject will only be allocated when entry of that subject to the randomized part of the trial has been confirmed.

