4 STUDY DESIGN

4.1 OVERALL DESIGN

Opioid analgesics are prescribed for moderate to severe pain disorders; however, there are contraindications and side effects that are common to all opioids. We hypothesize using local regional anesthetic after sinus surgery will reduce pain, therefore decreasing the need for post-operative opioid consumption.

This is a Phase 4, randomized, single-blinded, single-site, parallel-assignment intervention with a primary purpose of supportive care after functional endoscopic sinus surgery (FESS). It is anticipated that 30 subjects will be enrolled in this protocol. Potential subjects will be male or female adults over the age of 18 from the United States who undergo functional endoscopic sinus surgery (FESS) under the supervision of one surgeon.

Potential participants will be approached during their regularly-scheduled clinic visit about participation in the study. If they agree to participate, they will sign an informed consent form. During the baseline visit, demographic information, medical history, concomitant medications, vital signs, height, and weight will be collected. A routine nasal endoscopy will be performed to assess the need for surgical intervention, and routine CT sinus scans will be obtained and/or reviewed.

Participants will be randomized to one of the two following groups:

- **Treatment Group (n = 15):** participants will receive 20 mL of 1.3% bupivacaine with 2 mg dexamethasone injected locally in the location for sensory nerves of the sinus cavities and face during the FESS procedure
- **Control Group (n = 15):** participants will not receive regional anesthetic during the FESS procedure

Participants will have their scheduled functional endoscopic sinus surgery procedure. After surgery, participants will be given a pain diary to record their pain score on a scale of 1-10, and a place to record their use of opioids, as well as over-the-counter non-steroid anti-inflammatories such as acetaminophen and ibuprofen. Participants will record their scores and drug use daily for 10 days post-surgery. At their first post-operative clinic visit, the diary will be reviewed, and their opioid use will also be evaluated by counting the pills left on their prescription.

Data points/variables to be collected during the study could include the following, to be ascertained from the medical record and/or patient report:

- Name
- Medical Record Number
- Age
- Gender
- Type of surgery
- Duration of surgery

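### Section 6.2 fixes the order of allocation but does not keep the schedule from those who recruit, schedule or operate, so foreknowledge of the next assignment cannot be ruled out

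*Protocol*

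**What the plan says.** Section 6.2 of the Protocol is the whole allocation procedure, in three sentences.

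- The ratio: "Subjects will be randomized 1:1 (parallel assignment) into the two treatment groups".
- The mechanism: the next subject "will receive the treatment corresponding to the next free number in the randomization schedule".
- The timing: number and treatment "will only be allocated when entry of that subject to the randomized part of the trial has been confirmed".

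Other sections set the conditions in which this operates.

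- Section 4.1 describes a single-blinded, single-site trial with one supervising surgeon. On size it says "It is anticipated that 30 subjects will be enrolled in this protocol", with 15 planned per arm.
- Section 4.3 says controls are not injected.
- Section 5.4, on recruitment: "Potential subjects will be approached by the Principal Investigator or qualified research staff".
- Sections 1.2 and 8.1 place randomization on the day of surgery.
- Section 7.2, on replacement: "Subjects who sign the informed consent form and are randomized but do not receive the study intervention may be replaced". Those treated and later withdrawn will be replaced. No one is named as deciding, and no rule is given for the replacement's number.
- Section 7.1 turns subjects who discontinue the intervention into screen failures and drops them from the data, although section 5.3 defines screen failures as people never randomized or entered.

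**The concern.** Section 6.2 controls when a number is used, not who can know what it is. A schedule pinned up in the clinic would comply with all three sentences.

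Someone who can read or guess the next assignment can influence who receives it, for example through whether or when a patient's entry is confirmed, or through the order of cases on a day. The resulting difference between arms exists before any treatment is given. Analysis cannot reliably remove it, because the reasons for steering are usually not recorded. With 30 patients and self-reported pain as the primary endpoint, a few steered patients could tilt the comparison.

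Concealment governs conduct before any data exist. It belongs in this section of the protocol and is not a detail normally left to an analysis plan.

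**Working it through.** **Inputs from the Protocol.** Ratio 1:1 (6.2); 30 planned, 15 + 15 = 30 (4.1); past assignments known to the operating team, since controls are not injected (4.3).

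**Assumptions.** The documents do not state how the sequence is restricted. I take it as balanced, in one list of 30 or in blocks of 2 to 10. A coin toss for each patient would give exactly 15/15 with probability C(30,15)/2^30 = 155,117,520/1,073,741,824 = 0.144. The planned 15 and 15 therefore suggest a restricted list but do not prove one.

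**Step 1: correct guesses.** The guesser always names the arm that is behind and tosses a coin at ties. For a balanced sequence of length 2m the expected number correct is

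m + ½ × (4^m / C(2m, m) − 1).

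For m = 15: 15 + ½ × (6.922 − 1) = 17.96, against 15 by chance.

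**Step 2: assignments known with certainty.** These are the ones left after one arm of the list or block is full. The expected number is 2m/(m + 1). For m = 15: 30/16 = 1.875.

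**Step 3: range over the unstated restriction.** Per-block results are scaled to 30 patients.

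| Restriction | Correct of 30 | Share | Certain of 30 |
|---|---|---|---|
| Unrestricted | 15 | 50% | 0 |
| One 15/15 list | 17.96 | 59.9% | 1.9 |
| Blocks of 10 | 19.6 | 65.3% | 5 |
| Blocks of 6 | 20.5 | 68.3% | 7.5 |
| Blocks of 4 | 21.25 | 70.8% | 10 |
| Blocks of 2 | 22.5 | 75.0% | 15 |

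The last column requires that the list total or block size is known; the guessing columns do not. Thirty is not a multiple of 4, so that row is a rate. Seven full blocks plus the first two places of an eighth give 7 × 2.833 + 0.5 + 0.667 = 21.0 correct.

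**Step 4: undisclosed, varying small blocks.** Simulation of 30 assignments with block sizes drawn at random gives about 20.6 correct for sizes 4/6, 21.0 for 2/4/6 and 20.2 for 4/6/8. All exceed the 17.96 of a single list. Hiding the block sizes does not help, because the guess needs only the running count.

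**Step 5: a longer list.** For a permuted list of length 2m > 30, of which 30 places are used, the expected number correct is the sum over i = 0 to 29 of E[larger remaining arm]/(2m − i). With a 20/20 list, as an example, simulation gives about 16.5 of 30.

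**The case against.** The best defence is the last sentence of section 6.2: no number is drawn before entry is confirmed, so nobody can look at the draw and then decide on entry. That is a real safeguard and it stands. It does not help if the next line can already be read or guessed when entry is being confirmed.

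The route for steering is also narrow. Consent and baseline come at a clinic visit, and randomization follows on the day of an operation already scheduled. The number that is next when a patient is approached need not be that patient's number. This too stands: the documents show that steering is possible, not that it is likely.

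Four stronger readings are tempting, and the documents do not support them.

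- *The investigator sees the schedule.* The Protocol is silent on who holds it. That all 30 assignments would be known from an open list is true but hypothetical.
- *One person recruits, operates and decides replacements.* Section 5.4 shares recruitment with research staff, section 4.1 does not identify the surgeon as the Principal Investigator, and section 7.2 names no decider. Overlap is allowed but not stated.
- *A replacement's arm is known in advance.* That would need replacement within arm, which is not stated. The only rule given is the order in section 6.2.
- *Randomization is the only protection against bias.* Section 4.1 also calls the trial single-blinded, though section 4.2 concedes that control patients may notice they were not injected.

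Finally, 15 per arm is a planned size, with 30 anticipated, so the totals are not strictly fixed. The running-count figures are conditional for that reason.

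**Conclusion.** The point holds as a gap in concealment: section 6.2 orders the allocation but does not separate the schedule from those who could act on it. It does not show that anyone has seen the list or steered entry.

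Assuming a hidden but balanced list and an operating team that remembers past assignments, the next arm can be guessed 60% to 75% of the time, depending on the unstated restriction. The low end, 18.0 of 30 with 1.9 certain, belongs to a single 15/15 list. These figures measure predictability. They are not an estimate of bias in the treatment effect, for which the documents give no basis.

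The rules for replacement and removal in sections 7.1 and 7.2 are a related weakness. They act after randomization and are a separate problem from selection at entry, but they leave unclear whether an assignment, once revealed, is binding.

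This should be changed. The remedy is cheap, and the harm cannot be repaired afterwards.

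**What to change.** Amend section 6.2 as follows.

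- A person who neither recruits nor operates generates and holds the schedule.
- The list is unrestricted, or is one permuted list longer than 30 with its totals undisclosed. Small blocks are not used, even with varying undisclosed sizes.
- Assignments are kept in sequentially numbered opaque sealed envelopes or a locked module. Each is opened for a named patient, only after entry is confirmed, and logged with a time stamp.
- Opening is at one fixed moment, the same for both arms and before their care differs. It cannot be tied to the injection: controls receive none, and sections 6.1.2 and 4.2 disagree on whether it is given during or after surgery, which must be reconciled separately.

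Align sections 7.1 and 7.2 with this. A patient whose envelope has been opened counts as randomized and is not reclassified as a screen failure. Any replacement takes the next unopened number.

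The cost is protocol wording, a set of envelopes or a simple module, and some time from an independent member of staff. Sealing alone does not remove inference from the running count, which is why the type of list matters. The downside is that final arm sizes may differ from 15/15. With an unrestricted list the standard deviation of one arm's size is √(30 × 0.5 × 0.5) = 2.7 patients.
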